- Subjects will receive a single dose of MVA-NSmut vaccine or placebo per randomized assignment via intramuscular injection in the deltoid muscle of the preferred arm. Following vaccination the injection site will be covered with a sterile dressing and subjects will be observed in the clinic for at least 30 minutes. The vaccination site will be examined, and any AE/SAEs will be assessed prior to discharge from the clinic.
- Subjects will be provided with a memory aid and other study related materials to record daily oral temperature and systemic and local AE/SAEs. Subjects will be encouraged to take their temperature around the same time each day. Subjects will be instructed on how to use the memory aid and how to measure and record AE/SAEs prior to discharge from the clinic. Subjects will be instructed to notify the study center if they develop any severe reactions following vaccination. If the site principal investigator or appropriate sub-investigator deems the reaction severe enough, s/he will give further instructions on the proper course of action, including a return to the clinic for immediate evaluation if appropriate.
- Counseling on avoidance of HCV and HIV infection, and pregnancy will be conducted.
- Referral to drug treatment and needle exchange programs will be provided.

• Subjects who become HCV PCR+ after the 1st vaccine may receive a 2nd vaccine dose. These subjects will return for their Visit 7 and 8 assessments and follow the Confirmed HCV Infection visit schedule outlined in Appendix D.

8.2.6 Day 59 [Target 3 Days Post Second Vaccination], Visit 7

(Window: 1-5 days after receipt of second dose of vaccine)

- Current health status will be reviewed and any changes since the last visit will be noted.
- The vaccination site will be examined.
- A targeted physical examination may be performed, if indicated, based on review of current health status.
- Study personnel will review the memory aid information with the subject and record all AE/SAEs and concomitant medications on the appropriate data collection form.
- Counseling on avoidance of HCV and HIV infection, and pregnancy will be conducted.
- Referral to drug treatment and needle exchange programs will be provided.

8.2.7 Day 63 [Target 7 Days Post Second Vaccination], Visit 8

(Window: 7-21 days after receipt of second dose of vaccine)

- Current health status will be reviewed and any changes since the last visit will be noted.
- The vaccination site will be examined.

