The first stage of the study is designed to establish the safety and immunogenicity of the sequential administration of the AdCh3NSmut1 and MVA-NSmut vaccines in a prime/boost regimen in the target population. The first interim analysis will focus on presenting descriptive tabulations of the safety parameters to the DSMB along with the ELISpot assay immunological data. The immunological data analysis will not require study un-blinding. A positive immune response is defined by two criteria: i) more than 48 spot forming cells per million PBMC; ii) at least three times the mean background spots per million PBMC found in ELISpot wells containing cells and peptide diluent (DMSO).^{39,87,88} A subject will be considered to be a responder if a positive immune response is detected in at least one of six different pools of peptides utilized from at least one of the blood samples drawn after the first or second vaccination. Please note that results obtained from blood samples drawn after the onset of HCV infection will not be used in this first interim analysis. A subject will be considered evaluable for the first interim immunological analysis if ELISpot assay data is available from a sample drawn 7-21 days after receipt of the second vaccination, the anticipated timeframe in which a positive response to vaccine will be detected if present. Note that this requirement does not alter the definition of a responder provided above, and in particular, a positive ELISpot result after the first vaccination still suffices to define a responder. The study will proceed to Stage 2 in the absence of any safety concerns and if at least 30% of the evaluable subjects in Stage 1 of the study ($n = 68 \pm 4$) have a positive immune response to HCV. If this threshold is not met, then a more complete unblinded analysis of immunogenicity responses will be undertaken by an independent assessor appointed by DMID.

As noted in the section 11.2 (Sample Size Considerations), the statistical information goal for the efficacy endpoint of prevention of chronic HCV is 43 cases of chronic HCV in the per protocol analysis cohort. At the second interim analysis, the DSMB will do a blinded examination of progress towards this goal, and decide whether to recommend an extension of the enrollment period, while it is still possible to do so without halting enrollment and losing momentum in accrual.

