3. STUDY OBJECTIVES AND ENDPOINTS

3.1. Study Objectives

The primary safety objective is:

1. To assess the safety of new candidate hepatitis C virus vaccines, AdCh3NSmut1 and MVA-NSmut, compared to placebo when administered sequentially to IDUs.

The primary efficacy objective is:

1. To determine if AdCh3NSmut1 and MVA-NSmut HCV vaccines will reduce incidence of chronic HCV infection compared to placebo among HCV-uninfected IDUs

The secondary immunogenicity objective is:

1. To evaluate the immunogenicity of the new candidate hepatitis C virus vaccines, AdCh3NSmut1 and MVA-NSmut, compared to placebo when administered to HCV-uninfected IDUs.

The exploratory efficacy objectives are:

1. To determine if AdCh3NSmut1 and MVA-NSmut HCV vaccines will reduce incidence of incident HCV infection compared to placebo among HCV-uninfected IDU.
2. To determine if AdCh3NSmut1 and MVA-NSmut HCV vaccines will reduce 9-month incidence of chronic HCV infection compared to placebo among HCV-uninfected IDU.
3. To determine if AdCh3NSmut1 and MVA-NSmut HCV vaccines will reduce peak concentration (magnitude) of HCV RNA compared to placebo, in blood samples of persons with incident HCV infection.
4. To determine if AdCh3NSmut1 and MVA-NSmut HCV vaccines will reduce duration of HCV viremia (shorter time to spontaneous resolution) during incident infection (6-month period following incident HCV infection) compared to placebo in blood samples of persons with incident HCV infection.
5. To determine if AdCh3NSmut1 and MVA-NSmut HCV vaccines will reduce incidence of chronic HCV infection with genotype 1 compared to non-genotype 1 among HCV-uninfected IDU.

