3.2. Endpoints

The primary safety endpoints are as follows:

1. Occurrence of vaccine-related serious adverse events (SAEs) from the time of first vaccination through the entire study period.
2. Occurrence of severe local and/or systemic solicited reactogenicity signs and symptoms in the 8 days (Day 0-7) after each vaccination.
3. Occurrence of clinical safety laboratory adverse events (AEs) assessed at baseline and 1 month following each vaccination.

The occurrence of these safety parameters will be assessed by treatment group (vaccine and placebo).

The primary efficacy endpoint is:

1. Chronic HCV infection at 6 months defined by persistent viremia over a period of 6 months after detection of incident infection.

The secondary immunogenicity endpoint is:

1. The frequency of positive cell mediated immune response within 14 days after the last vaccination by treatment group (vaccine vs. placebo)

The exploratory efficacy endpoints are as follows:

1. An incident HCV infection will be defined as a new confirmed positive HCV RNA test after a previous negative HCV RNA test. The interval during which incident HCV infection occurs will be defined by the date of the last documented negative HCV RNA results, and the date of the first positive HCV RNA result.
2. Chronic HCV infection at 9 months defined by persistent viremia over a period of 9 months after detection of incident infection.
3. Quantitative viremia measures, including the incident peak and total HCV RNA levels detected, from the date of first HCV RNA detection and at study visits in the first 6 months of viremia will be compared, between vaccinated and placebo groups, using logarithmic IU/mL values.
4. The duration of incident infection will be defined as the interval between incident HCV infection and viral clearance. For subjects who do not clear HCV viremia, the duration will be measured as six months following incident infection. The interval during which incident HCV infection occurs will be defined by the date of the last documented HCV RNA negative results, and the date of the first positive HCV RNA result. The interval during which viral clearance occurs will be defined by the date of the last test with detectable HCV RNA and the first of two consecutive samples with undetectable HCV RNA.

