6.3.4. Immunogenicity Population

The immunogenicity analysis population will consist of all subjects who received any study product and for whom immunogenicity endpoint data are available. If a subject does not receive the second dose, the subject will not be included in the Post-Dose 2 analyses. In the unlikely event of an error in randomization or study product administration (i.e., incorrect product), subjects will be grouped by the product they actually received. In the unlikely event that a subject receives one dose of vaccine and one dose of placebo, the subject will be excluded from immunogenicity analyses.

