10. IMMUNOGENICITY

The secondary objective of this study is to evaluate the immunogenicity of the AdCh3NSmut1 and MVA-NSmut vaccines compared to placebo when administered to HCV-uninfected IDUs. To assess this, the frequency of positive cell mediated immune responses within 14 days after the last vaccination will be compared between the vaccine and placebo groups.

The primary assay to monitor vaccine immunogenicity is the IFN- γ ELISpot, which will be performed at time points indicated in the study visit flow chart in Section 4.5. Samples are run in triplicate; thus, each pool of peptides will have three responses. In addition, the ELISpot data is reported from the lab in spots per 200,000 PBMC. Thus, in calculating an individual's pool-specific response, the raw data for a pool will be multiplied by five and then averaged across the triplicates. The negative control, DMSO, is also analyzed (in triplicate). Thus, to correct for background for each individual, the average of the triplicate DMSO responses will be subtracted from each of the averaged pool responses. All analyses of ELISpot data will use the averaged and background-corrected responses. Pool-specific summaries will use the following labels: NS3p, NS3h, NS4, NS5a, NS5bI, and NS5bII (these labels correspond to the following peptides, respectively: NS3 protease aa 1027-1349, NS3 helicase aa 1339-1661, NS4 aa 1655-1977, NS5a aa 1971-2425, NS5bI aa 2415-2725, and NS5b aa 2715-3011). In addition, for Visit 26 summaries, the following five pools will also be included in pool-specific summaries: Core, E1, E2, p7, and NS2. These additional pools will not be used for summaries that combine pools.

A positive immune response is defined by two criteria:

- i. more than 48 spot forming cells per million PBMC;
- ii. at least three times the mean background spots per million PBMC found in ELISpot wells containing cells and peptide diluent (DMSO) [13,14,15].

An individual will be considered a responder if a positive response to at least one in 6 mixtures (pools) of peptides is detected. The number of responders and response rate with associated 95% confidence interval will be summarized by treatment group (Table 116).

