Program type:	Methadone detox	x	x	x	x	x	x	x	x
	Methadone maintenance	x	x	x	x	x	x	x	x
	Suboxone detox	x	x	x	x	x	x	x	x
	Suboxone maintenance	x	x	x	x	x	x	x	x
	Residential Treatment	x	x	x	x	x	x	x	x
	NA, AA, or other 12-step program	x	x	x	x	x	x	x	x
	Medically-assisted residential detox	x	x	x	x	x	x	x	x
	Non-medically assisted residential detox	x	x	x	x	x	x	x	x
	Other	x	x	x	x	x	x	x	x
	Total subjects receiving treatment	x	x	x	x	x	x	x	x
Reason(s) for treatment:	Alcohol	x	x	x	x	x	x	x	x
	Heroin	x	x	x	x	x	x	x	x
	Other opioids or painkillers	x	x	x	x	x	x	x	x
	Other sedatives	x	x	x	x	x	x	x	x
	Cocaine or crack	x	x	x	x	x	x	x	x
	Amphetamines	x	x	x	x	x	x	x	x
	Cannabis	x	x	x	x	x	x	x	x
	Inhalants	x	x	x	x	x	x	x	x
	Other	x	x	x	x	x	x	x	x

Table 115: Summary of Substance Treatment by Treatment Group—Safety Population

		Vaccine (N=X)		Placebo (N=X)		All Subjects (N=X)	
		n	%	n	%	n	%
Program type:	Methadone detox	x	x	x	x	x	x
	Methadone maintenance	x	x	x	x	x	x
	Suboxone detox	x	x	x	x	x	x
	Suboxone maintenance	x	x	x	x	x	x
	Residential Treatment	x	x	x	x	x	x
	NA, AA, or other 12-step program	x	x	x	x	x	x
	Medically-assisted residential detox	x	x	x	x	x	x
	Non-medically assisted residential detox	x	x	x	x	x	x
	Other	x	x	x	x	x	x
	Total subjects receiving treatment	x	x	x	x	x	x
Reason(s) for treatment:	Alcohol	x	x	x	x	x	x
	Heroin	x	x	x	x	x	x
	Other opioids or painkillers	x	x	x	x	x	x
	Other sedatives	x	x	x	x	x	x
	Cocaine or crack	x	x	x	x	x	x
	Amphetamines	x	x	x	x	x	x
	Cannabis	x	x	x	x	x	x
	Inhalants	x	x	x	x	x	x
	Other	x	x	x	x	x	x

Section 14.3 Immunogenicity Data**Table 116: ELISpot Responses by Treatment Group—Immunogenicity Population**

	Vaccine (N=X)	Placebo (N=X)
Number of Responders	xxx	xxx
Response Rate ^[1]	xx.x	xx.x
95% Confidence Interval	xx.x, xx.x	xx.x, xx.x
[1] Response Rate is calculated as the number of subjects with a positive ELISpot/N * 100%.		

Table 117: Geometric Mean (GM) and Geometric Mean Fold Rise (GMFR) ELISpot Responses (Across all Pools) with 95% Confidence Intervals by Study Day and Treatment Group—Immunogenicity Population, HCV- Subjects

Time Point	Statistic	Vaccine (N=X)	Placebo (N=X)
Day 1 (Dose 1)	n	x	x
	GM	x.x	x.x
	95% CI	x.x, x.x	x.x, x.x
Day 30	n	x	x
	GM	x.x	x.x
	95% CI	x.x, x.x	x.x, x.x
	GMFR	x.x	x.x
	95% CI	x.x, x.x	x.x, x.x
Day 56 (Dose 2)	n	x	x
	GM	x.x	x.x
	95% CI	x.x, x.x	x.x, x.x
	GMFR	x.x	x.x
	95% CI	x.x, x.x	x.x, x.x
...			

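### Table 116, the secondary immunogenicity result, pools subjects already HCV-infected at the post-boost sample, so infection-induced T-cell responses can count as responders

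*SAP*

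**What the plan says.** The secondary endpoint (SAP 3.2) is the frequency of a positive cell-mediated response within 14 days after the last vaccination, vaccine versus placebo. SAP 6.3.4 sets the population: "The immunogenicity analysis population will consist of all subjects who received any study product and for whom immunogenicity endpoint data are available". Subjects who miss dose 2 leave the post-dose-2 analyses, but HCV infection is not a reason for exclusion. By contrast, the mITT population (SAP 6.3.2) excludes infection at the first vaccination, and the ATP population (SAP 6.3.3, criterion d) excludes infection before the second.

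SAP 10 calls a subject a responder if at least one of six NS pools is positive, and summarises the rate by treatment group in Table 116. The shell has one Vaccine and one Placebo column, with no HCV-status row and no time point. Its footnote reads: "Response Rate is calculated as the number of subjects with a positive ELISpot/N * 100" percent. SAP 10 then calls for separate HCV-negative and HCV-positive results, but for the further summaries listed there (Tables 117 to 123 and their figures).

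Protocol 8.2.5 states: "Subjects who become HCV PCR+ after the 1st vaccine may receive a 2nd vaccine dose". These subjects return for Visits 7 and 8, and Visit 8 includes an immunology draw (Protocol 8.2.7). For Stage 1, Protocol 11.3 states that "results obtained from blood samples drawn after the onset of HCV infection will not be used in this first interim analysis". Neither Protocol 11.4.4 nor SAP 10 repeats that rule for the final analysis.

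**The concern.** The six pools span NS3 to NS5b, which natural infection also presents to T cells. Protocol 2.1, on the rationale for the NS antigen, reports T-cell responses in HCV-infected people when peptides of the vaccine sequence are used. A placebo subject infected in the first eight weeks can therefore be ELISpot-positive at Visit 8 with no vaccine exposure, and Table 116 would count that subject as a responder.

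The effect is uneven across arms. Early infections should be about equally common in both, but most vaccinees are expected to respond anyway: Protocol 2.2.3 reports that all did at this AdCh3NSmut dose in the earlier trial. Infection therefore adds responders mainly in placebo. At stake are the two published response rates, their confidence intervals and the difference between them.

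**Working it through.** The documents give no sizing or expected rate for this endpoint, so there is no plan figure to reproduce. The check estimates how many subjects are affected and how far the rates move.

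**Inputs from the documents**
- Incidence of primary HCV infection: 27 per 100 person-years (Protocol 11.4.5, item 1). Range: 10% to 30% annualised (Protocol 2.1; SAP 2), treated here as rates per 100 person-years.
- Dose 2 at Day 56 and Visit 8 at target Day 63. RNA is tested at Days 30, 56 and 90 (Protocol Appendix C).
- 270 subjects per arm (SAP 4.1).

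**Assumptions**
- Incidence is equal in both arms and counted from Day 0, and everyone infected takes dose 2 and gives the sample.
- r, the probability that an infected subject is ELISpot-positive, is 0.5 to 1.
- True response rate p is 60% to 95% in the vaccine arm and 0% in placebo (0% to 5% for the power check).

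**Share infected by dose 2:** s = 1 − exp(−rate × 56/365.25).

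| Rate per 100 PY | s | Per arm (× 270) |
|---|---|---|
| 10 | 1.5% | about 4 |
| 27 | 4.1% | about 11 |
| 30 | 4.5% | about 12 |

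**Effect on the responder rate:** rise = (1 − p) × s × r.
- Placebo, p = 0, r = 1: the rise equals s, so 1.5 to 4.5 points (4.1 at 27 per 100 PY). With r = 0.5 at 27 per 100 PY it is 2.0 points.
- Vaccine at 27 per 100 PY, r = 1: 0.40 × 4.06 = 1.6 points if p = 60%; 0.05 × 4.06 = 0.2 points if p = 95%.
- Difference, true 80% versus 0%, at 27 per 100 PY and r = 1: 80 + 0.20 × 4.06 − 4.06 = 76.8 points.

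**Response lag.** If a detectable response takes four weeks (assumed), only infections by Day 35 matter at Day 63: 1 − exp(−0.27 × 35/365.25) = 2.6%, about 7 per arm.

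**Significance test.** With 270 per arm and the assumed true rates, power stays about 1.00. This holds even at 30 per 100 PY over 107 days (30 days from screening plus Day 77), where 8.4% are infected.

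**What an infection-date rule removes.** SAP 3.3.3 dates infection at the midpoint between the last negative and first positive RNA test. A subject negative at Day 56 and positive at Day 90 is dated (56 + 90)/2 = Day 73. That is after Visit 8 (Day 63) and after the 14-day limit (Day 70). On target days the rule therefore removes subjects positive at Day 30 or Day 56 and no others. Infections between Day 56 and Day 63 stay in: at 27 per 100 PY, 4.55% − 4.06% = 0.5%, about one per arm.

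**The case against.** The strongest reply is that the omission is small, visible and harmless to inference. The bias works against the vaccine and the test is unaffected. Table 121 shows positive pools by study day in HCV-negative subjects, and Listings 23 and 24 give subject-level ELISpot data and the first positive day. Infected subjects only may receive dose 2, recent infections may not yet give a response, and 27 per 100 person-years is near the top of the quoted range. All of this stands and is why the size is stated as an upper figure. It does not settle the matter: Table 121 reports means, medians and ranges rather than a responder rate, and the endpoint table would still carry the mixed figure.

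A second reply is also fair: infection is a post-randomisation event that the vaccine may affect (exploratory objective 1), so removing infected subjects departs from a comparison of all randomised subjects. That is a reason to keep the all-subjects rate beside the restricted one.

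A reader might infer that SAP 6.3.4 contradicts the objective, worded "compared to placebo when administered to HCV-uninfected IDUs". It does not. SAP 4.1 defines uninfected as negative at screening, and the efficacy objective uses the same term for people whose later infection is the endpoint.

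**Conclusion.** The point holds as a bias in reported rates. Followed as written, Table 116 mixes vaccine-induced and infection-induced responses. The placebo rate could be raised by at most about 1.5 to 4.5 points and the vaccine rate by less, so the difference is understated. This rests on the protocol's incidence figures, equal incidence by arm, infections counted from Day 0, and full reactivity without lag; partial reactivity or a lag makes it smaller.

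Four stronger readings are not supported:
- **The significance test is at risk.** Power stays about 1.00 under every assumed scenario with 270 per arm.
- **The final rate loses comparability with Stage 1.** The two were never comparable. The interim was blinded, pooled across arms, counted a response after either dose, and served a 30% threshold (Protocol 11.3).
- **Pre-existing responses at Day 0 distort the result.** The evidence is the title of a cited reference. Randomisation should balance such responses, and Tables 117 to 122 include the dose-1 day.
- **The table counts anyone ever positive.** At 27 per 100 person-years, 35.8% would be infected by Day 600. Although the shell gives no time point, SAP 3.2 and SAP 10 fix the 14-day window.

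**What to change.** In SAP 6.3.4 and SAP 10, and in the Table 116 shell:

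1. State that Table 116 uses the ELISpot sample drawn within 14 days after the last vaccination. The Visit 8 window runs to 21 days after dose 2, so the shell needs to say this.
2. In the main row, exclude samples drawn on or after the HCV infection date defined in SAP 3.3.3. In practice this removes subjects RNA positive at Day 30 or Day 56.
3. Keep the rate in all subjects as a supporting row, because infection occurs after randomisation.

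All the data are already collected, and the wording can be fixed before unblinding. The cost is about 2% to 5% fewer subjects in the main row and one extra row. Nothing here concerns whether infected subjects should receive dose 2.

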6.4. Covariates and Subgroups

As described in Section 4.4.2, the randomization of treatment assignments and the primary analysis will be performed as stratified by gender and IL28B status. Randomization is also stratified by clinical site, however given that the University of New Mexico was added late in enrollment (first enrollment 16 November 2015); stratifying analyses by site in addition to gender and IL28B may result in insufficiently sized strata. Thus, efficacy analyses will not be stratified by site and safety analyses will be separately stratified by site.

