5.3 Randomization and Code Breaking Procedures

The list of randomized treatment assignments stratified by gender and IL28B status will be prepared by statisticians at The Emmes Corporation and included in the enrollment module of The Emmes Corporation's Internet Data Entry System (IDES). IDES will assign each subject a treatment code from the list after demographic and eligibility data have been entered into the system. A designated individual at each site will be provided with a treatment key, which links the treatment code to the actual treatment assignment, which will be kept in a secure place.

Instructions for use of the enrollment module are included in the IDES User's Guide. Manual back-up randomization procedures are provided for use in the event that the site temporarily loses access to the Internet or the online enrollment system is unavailable.

Unblinding

Unblinding is unlikely to be necessary for the provision of medical treatment or to otherwise protect the safety of study subjects. In the event that an investigator is concerned that a subject might be put at undue risk by continuing product use, the investigator may discontinue product use by this subject; however, knowledge of the specific product (vaccine or placebo) to which the subject was assigned should not be necessary to guide further follow-up and/or treatment.

The co-principal investigators and/or Independent Safety Monitor (ISM) should be available to review and evaluate any notable reactions. In the case of a medical emergency, the co-principal investigators or ISM may deem it medically necessary to unblind the subject's treatment assignment. If the co-principal investigators or ISM believe that unblinding would benefit the medical care of the subject and time permits, DMID will be consulted prior to unblinding, and concurrence will be obtained.

Otherwise, subjects will be unblinded to their drug only at the close of the trial. Subjects who develop HCV infections or drop out will not be unblinded early. The Data Safety and Monitoring Board (DSMB) may receive data in aggregate and presented by treatment group, but without the treatment group identified. The DSMB may be unblinded to individual study treatment assignments, as needed, to adequately assess safety issues.

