4.4.2. Method of Assigning Subjects to Treatment Groups (Randomization)

Enrollment of subjects is done online using the enrollment module of the EDC, maintained by the SDCC. Eligible subjects are randomized and assigned in a 1:1 ratio stratified by site, gender, and IL28B status, to receive AdCh3NSmut1 and MVA-NSmut HCV vaccines or placebo at Day 0 and Day 56 after providing consent and confirmation of eligibility with the study inclusion and exclusion criteria.

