5. SAMPLE SIZE CONSIDERATIONS

Sample size calculations are based on the assumption of detecting a 60% reduction in incidence of chronic infection over 18 months of post-vaccination follow-up among vaccinated subjects compared to unvaccinated controls in an according to protocol (ATP) analysis. A total of 43 observed events of chronic infection in the ATP cohort would provide power of 85% for a two-sided log rank test conducted at the significance level (alpha) of 0.05 to detect a 60% reduction in hazard rate. The incidence of chronic infection among controls is assumed to be 14% annually [10]. Assuming 14 cases/100 person-years (PY) in the control group, and 5.6 cases/100 PY in the vaccine group, a total of 292.5 subjects in the ATP cohort followed for 1.5 years would provide on average 43 events. We further assume that 65% of enrolled subjects will be retained in the ATP cohort. Therefore, we inflate the required number of subjects by a factor of $1/0.65$ and obtain a target enrollment of 540 subjects, or 270 subjects per vaccination group.

The original enrollment target of the study was 344 subjects. At the April 29, 2014 DSMB meeting, the DSMB reviewed the progress towards the goal of 43 observed events of chronic infection in the ATP cohort and recommended increasing the target enrollment from 344 to 450, or 225 subjects per vaccination group.

At the September 2, 2015 DSMB meeting, the DSMB reviewed the progress towards the goal of 43 observed events of chronic infection in the ATP cohort and recommended increasing the target enrollment from 450 to 540 subjects, or 270 subjects per vaccination group.

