6.7. Multicenter Studies

As described in Section 4.4.3 and Section 6.4, the randomization of treatment assignments and the primary analysis will be performed as stratified by gender and IL28B status. Randomization is also stratified by clinical site, however given that the University of New Mexico was added late in enrollment (first enrollment 16 November 2015); stratifying efficacy analyses by site in addition to gender and IL28B may result in insufficiently sized strata. Thus, efficacy analyses will not be stratified by site.

Though sites are using standardized procedures for vaccination and assessment of solicited and unsolicited adverse events, and the study relies on central laboratories for the assessment of immunogenicity and clinical efficacy endpoints, there is expected variation in the demographics and risk behavior in the patient population between sites, so site effects of safety data are expected. Estimates of site effects should be considered exploratory given that the study was not explicitly designed with enough power to detect site effects.

See Section 9 for descriptions of the by-site analyses for safety analyses.

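### Efficacy models leave out site although the SAP says randomisation was stratified by site: a small loss of power, not a validity problem

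*SAP*

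**What the plan says.** **Randomisation.** SAP 4.4.2 states that 1:1 allocation is "stratified by site, gender, and IL28B status". SAP 6.4 and 6.7 also say that site is a randomisation stratum. Protocol 5.3 does not name it: "The list of randomized treatment assignments stratified by gender and IL28B status will be prepared by statisticians". Protocol 4 and SAP 4.1 also list only gender and IL28B. SAP 14, which records changes, does not mention the difference. SAP 6.7 points to SAP 4.4.3 for the randomisation, but that section covers dose selection.

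**Analysis.** SAP 6.4: "Thus, efficacy analyses will not be stratified by site and safety analyses will be separately stratified by site". The reason given is that New Mexico joined late (first enrolment 16 November 2015), so strata formed from site, gender and IL28B could be too small. SAP 8.1 fits the primary Cox model with four gender by IL28B strata, as Protocol 11.4.3 specifies. The covariate-adjusted and Fine-Gray sensitivity models in SAP 8.1 and the models in SAP 8.3 have no site term either. Site enters the efficacy output only through the descriptive rates in Table 28.

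**Site differences.** SAP 6.7 says "there is expected variation in the demographics and risk behavior in the patient population between sites", and from this draws a conclusion about safety data only.

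**The concern.** A factor that is balanced by design and also predicts outcome belongs in the analysis model. Leaving it out has two effects in a Cox model. The hazard ratio is pulled slightly towards 1, because it is averaged over sites with different risk. The model variance also ignores the balance that stratified randomisation created, so the test tends to be conservative. Both cost power.

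Injection behaviour is the route of exposure for the primary endpoint, so the SAP's expectation that risk behaviour varies by site is a reason to think site could be prognostic for chronic infection. The small-strata reason does not settle the matter. Site can be entered as two indicators without adding any stratum, and SAP 8.1 already uses that device when a sensitivity model enters gender and IL28B as fixed effects. What is at stake is power in a trial planned around 43 events.

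**Working it through.** **1. The plan's own figure.** SAP 5 states: "A total of 43 observed events of chronic infection in the ATP cohort would provide power of 85% for a two-sided log rank test". Its alpha is 0.05 and its target effect is a hazard ratio of 0.40. The Schoenfeld formula then gives

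events = 4 × (1.960 + 1.036)² / (ln 0.40)² = 4 × 8.978 / 0.8396 = 42.8, rounded up to 43.

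Power at 43 events is Φ(√43 × 0.9163 / 2 − 1.960) = Φ(1.044) = 85.2%. The stated figure is reproduced.

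For expected events, SAP 5 takes these rates: "Assuming 14 cases/100 person-years (PY) in the control group, and 5.6 cases/100 PY in the vaccine group". It applies them to an ATP cohort of 292.5 with 1.5 years each. The arithmetic is 292.5 × 1.5 × (0.14 + 0.056)/2 = 43.0, which agrees with the SAP's 43.

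**2. Simulation of the omission.** From the documents: 1:1 allocation, hazard ratio 0.40 (or 1 under the null), 1.5 years of follow-up, 43 expected events, three sites.

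Assumed, because the documents do not give them:
- site shares 45/45/10% (the third site standing for New Mexico) and the site rate ratios in the table
- permuted blocks of 4 within site × gender × IL28B
- 30% female and 40% IL28B CC, neither affecting the hazard
- exponential event times and retention at random

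The baseline hazard was set in each scenario to give 43 expected events. There were 12,000 simulated trials per scenario in each of two cohorts: 540 randomised with 54% retained (292.5/540 = 0.542), and 293 randomised with all retained. Each range below spans the two cohorts.

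| Site rates | Power, as planned (4 strata) | Power, 12 strata | Power, 4 strata + site covariate | Gain from site covariate (points) | Type I error, as planned |
|---|---|---|---|---|---|
| 1:1:1 | 82.7-82.9% | 81.9-82.7% | 82.7-83.0% | 0.0-0.2 | 4.7-5.2% |
| 1:2:2 | 81.6% | 81.5-82.0% | 82.2% | 0.6 | 4.6-4.8% |
| 1:3:3 | 81.3-82.0% | 81.8-82.1% | 82.2-83.0% | 0.9-1.0 | 4.6-4.9% |
| 1:3:6 | 80.3-80.9% | 81.6-82.1% | 82.5-82.6% | 1.7-2.2 | 4.7-4.8% |
| 1:6:6 | 79.7-80.3% | 81.6-82.2% | 82.5-82.6% | 2.3-2.8 | 4.1-4.5% |

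The two models that include site had type I error of 4.7-5.4% throughout. Monte Carlo error is about 0.35 points on power and 0.2 on type I error. The three tests were run on the same simulated trials, so comparisons within a row are more precise than that. Simulated power with equal rates is about 83% rather than 85%, because the Schoenfeld formula is an approximation at a hazard ratio of 0.40.

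**3. A larger cohort.** With 351 ATP subjects (540 × 0.65) and 8,000 trials per setting, the planned test rejected under the null in 4.2% (1:3:3), 4.7% (1:3:5) and 4.0% (1:5:5).

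**4. Twelve strata.** Full stratification is 0.2-0.8 points below the planned model when site rates are equal, within about half a point of it at 2- to 3-fold differences, and 1.2-1.9 points above it at 1:3:6 and 1:6:6. It does not beat the covariate in any row.

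**The case against.** The planned model is prespecified in Protocol 11.4.3, followed in SAP 8.1, and disclosed with a reason in SAP 6.4 and 6.7. Neither document gives an infection rate or an enrolment share by site. The sentence on variation between sites in SAP 6.7 concerns safety. If rates do not differ there is nothing to gain, and gains above 2 points need differences of about 6-fold. On this view, choosing the slightly more efficient model is a matter of preference. Adding site also shifts the target slightly, to a hazard ratio conditional on site, and it means changing the protocol as well as the SAP.

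Most of this stands, and it limits the point to a minor one. It does not defend the omission, because the small-strata reason does not apply to a covariate and the covariate costs no power when rates are equal.

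Three stronger readings are tempting and are not supported:
- A reader might infer that ignoring a randomisation factor invalidates the primary test. It does not: type I error is at or a little below 5%.
- A reader might infer that the test is severely conservative. At 2- to 3-fold differences its rejection rate under the null is 4.2-4.9%, and it is near 4% only at about 5- to 6-fold.
- A reader might infer that all twelve strata must be used. At moderate site differences they bring little or nothing.

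**Conclusion.** The point holds as a minor one. Under the assumptions listed, leaving site out costs about 0.6 points of power at a 2-fold difference in site infection rates, about 1 point at 3-fold and 2 to 3 points at 6-fold. It costs nothing if site rates are equal. Type I error of the planned test is about 4.0-4.9% when rates differ.

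The size rests on site shares and rate ratios that the documents do not give. The conservatism also depends on site having been a randomisation factor. If Protocol 4 and 5.3 describe what was done, that part largely falls away, and only the ordinary gain from adjusting for a prognostic factor remains. The conflict over the randomisation factors needs resolving whatever the size of the effect, because as the documents stand a reader cannot tell how treatment was allocated.

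**What to change.** - In SAP 6.4, 6.7 and 8.1, keep the four gender × IL28B strata and add site as a fixed covariate (2 df) to the primary Cox model, for both ATP and mITT. Do not make twelve strata the primary model.
- Amend the Cox model in Protocol 11.4.3 to match. If the protocol cannot be changed, prespecify the site-adjusted model as a sensitivity row in Table 8.
- State which randomisation factors were actually used, and make Protocol 4 and 5.3 and SAP 4.1, 4.4.2, 6.4 and 6.7 agree. Correct the cross-reference in SAP 6.7 and record the change in SAP 14.

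Cost: one model term, SAP wording and a short protocol amendment, settled before unblinding. No new data are needed and there is no loss of power.
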